23 APPENDIX 5 – NURSE ASSESSMENT FORMS

Nurse Assessment Day 0

Subject Number:	
,	

Subjects use of usual product and method for dressing a wound.		
What dressings did subject use?		
	Yes	No
Did subject contort/ stretch to apply dressing?		
Did Subject need assistance?		
Could subject apply dressing without raising arms over their head?		
Did subject use additional equipment to dress their wound? eg. Scissors, pins, tape, mirror		
If yes, please specify		

CE-GAX001-01

V4.0

CR: 144

Nurse Assessment Day 21

Subject Number:	

Subjects use of HidraWear AX for dressing a wound.		
Did subject contort/ stretch to apply dressing?		
Did Subject need assistance?		
Could subject apply dressing without raising arms over their head?		
Did subject use additional equipment to dress their wound? eg. Scissors, pins, tape, mirror		
If yes, please specify		

CE-GAX001-01

V4.0

CR: 144

24 APPENDIX 6 DERMATOLOGY QUALITY OF LIFE INDEX

1.	Over the last week, how itchy , sore , painful or stinging has your skin been?	Very much A lot A little Not at all		
2.	Over the last week, how embarrassed or self conscious have you been because of your skin?	Very much A lot A little Not at all		
3.	Over the last week, how much has your skin interfered with you going shopping or looking after your home or garden ?	Very much A lot A little Not at all	Not relevant	
4.	Over the last week, how much has your skin influenced the clothes you wear?	Very much A lot A little Not at all	Not relevant	
5.	Over the last week, how much has your skin affected any social or leisure activities?	Very much A lot A little Not at all	Not relevant	
6.	Over the last week, how much has your skin made it difficult for you to do any sport ?	Very much A lot A little Not at all	Not relevant	
7.	Over the last week, has your skin prevented you from working or studying?	Yes No	Not relevant	
	If "No", over the last week how much has your skin been a problem at work or studying ?	A lot A little Not at all		
8.	Over the last week, how much has your skin created problems with your partner or any of your close friends or relatives ?	Very much A lot A little Not at all	Not relevant	
9.	Over the last week, how much has your skin caused any sexual difficulties?	Very much A lot A little Not at all	Not relevant	
10.	Over the last week, how much of a problem has the treatment for your skin been, for example by making your home messy, or bytaking up time?	Very much A lot A little Not at all	Not relevant	

CE-GAX001-01

V4.0

CR: 144

DERMATOLOGY LIFE QUALITY INDEX (DLQI) - INSTRUCTIONS FOR USE

The Dermatology Life Quality Index questionnaire is designed for use in adults, i.e. subjects over the age of

16. It is self-explanatory and can be simply handed to the subject who is asked to fill it in without the need for detailed explanation. It is usually completed in one or two minutes.

SCORING

The scoring of each question is as follows:

Very much scored 3

A lot scored 2

A little scored 1

Not at all scored 0

Not relevant scored 0

Question 7, 'prevented work or studying' scored 3

The DLQI is calculated by summing the score of each question resulting in a maximum of 30 and a minimum of 0. The higher the score, the more quality of life is impaired.

HOW TO INTERPRET MEANING OF DLQI SCORES

0-1 no effect at all on subject's life 2-5 small effect on subject's life

6 – 10 moderate effect on subject's life 11 – 20 very large effect on subject's life

21 – 30 extremely large effect on subject's life

CE-GAX001-01

V4.0

CR: 144

25 APPENDIX 7 – SUBJECT CHECK INS

Daily Check in with Subjects:

Each day, at 1pm, subjects will receive an email requesting them to check in with the researcher by answering 3 questions.

- 1. What is your temperature?
- 2. How many dressings did you use in the last 24 hours?
- 3. Any comments?

This check in should take less than 5 minutes to complete.

Subjects will be required to respond by 5pm each evening. If subject has not responded by 5pm, a reminder text message will be sent to them.

If subject does not respond within 24 hours, the research nurse will call the subject to check in and take answers over the phone.

Weekly Check in with Subjects:

On day 7 and 14 subjects will be asked to complete the Dermatology Quality of life survey and questions on Ease of use, comfort, pain and confidence, at home. A link to the surveys will be emailed to them at 1pm in the afternoon with their daily check in.

Subjects will be required to respond by 5pm each evening. If subject has not responded by 5pm, a reminder text message will be sent to them.

If subject does not respond within 24 hours, the research nurse will call the subject to check in and take answers over the phone.

CE-GAX001-01

V4.0

CR: 144

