2.4 Contraindications and Warnings

A full list of contraindications and warnings are provided in the IFU supplied with the device.

Contraindications: Known allergies to materials specified

Warnings: Do not use if you have known allergies to materials specified.

Warnings

- 1. The garment is not a wound dressing wound(s) should be fully covered by dressing(s).
- 2. If any unexpected discomfort or wound irritation occurs, please consult your doctor or nurse.
- 3. Do not use, if you have a known allergy or sensitivity to materials listed.

CE-GAX001-01

V4.0

CR: 144

Potential side effects: Dermatitis, infection and skin irritation or skin abrasion.

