4 RISKS AND BENEFITS

4.1.1 Risk Analysis

- Hidradenitis Suppurativa wounds can sometimes be colonised by non-pathogenic bacteria, and may appear to be infected. This is not a true infection. However, subjects will examined by research nurse to assess the wound and will be asked to record their temperature during the study to monitor for signs of infection. There will be a registered nurse overseeing all subject interactions and demonstrations to ensure the safety of subjects
- Garment could cause discomfort to the subject. In the case of any discomfort the subject is requested to remove the wound care product
- There is also a minor concern re allergies to certain materials and this will be included in the PIL and will be an exclusion criteria

Risk assessment for Hidramed vs Standard Adhesive dressing.

Risk level and likelihood rated 1-5, 1 being the lowest and 5 being the highest.

Hidrawear AX Garment

Risk	Cause	Level of Risk	Likelihood of Risk	Control
Skin Irritation	Allergic to garment	1	1	Discontinue use immediately
Unnecessary Pain	Difficult dressing site			Use product as instructed exactly.
				Discontinue use immediately
Subject distress and embarrassment	Dressing leaking or falling off.	1	1	Use product as instructed exactly
Physical contamination of wound	Thread or fibres from product retained in wound	1	1	Selected bonded fabric that does not fray/produce fibres.
				Users instructed to carry out daily visual inspection of wound.
				Discontinue use immediately

CE-GAX001-01

V4.0

CR: 144

Dressing Supplied During Study

Risk	Cause	Level of Risk	Likelihood of Risk	Control
Skin Irritation	Allergic to dressings	1	1	Discontinue use immediately
Localised infection	Misuse of dressings	3	1	Follow user instructions exactly. Discontinue use immediately
Septicemia	Misuse of dressings	5	1	Follow user instructions exactly. Discontinue use immediately
				Monitor temperature twice daily during pilot period.
Subject distress and embarrassment	Dressing leaking or falling off.	1	1	Use product as instructed exactly

Standard Adhesive Dressing

Risk	Cause	Level of Risk	Likelihood of risk	Control
Skin Irritation	Allergic to or reaction to adhesive in dressing	1	3	Discontinue Use immediately
Localised infection	Misuse of dressings	3	3	N/A user instructions do not specify
Septicemia	Misuse of dressings	5	1	N/A user instructions do not specify
Unnecessary pain	Difficult dressing site, Adhesive damage to skin	5	4	N/A

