4.6 Steps to be Taken to Control or Mitigate Risks

Users will be assessed by a Research Team member to establish that no infection is present in the wound site on enrolment and assessment.

Subjects will be asked to measure and record their temperature daily and to contact nurse support if there is an elevation in temperature.

If subjects record a pyrexia greater than 38 degrees. The Subject will contact the Research team where it will be recorded. Subject will be asked to recheck temperature following 1 hour without temperature reducing medication (paracetamol ibuprofen et). If pyrexia persists, subject will be directed to attend GP for immediate follow up and the use of the study device will be stopped.

Research nurse to assess whether pyrexia is device related.

If it is not device related, a telephone contact log is to be filled in and reported to the sponsor.

[figure not shown]
If it is device related, an adverse is to be recorded and reported to sponsor

CE-GAX001-01

V4.0

CR: 144

Process Flow for Pyrexia >38 Degrees

The dressing used in this study is provided sterile.

The fastener used in this study is used externally and does not touch the skin during use. Material base and Velcro is medical grade.

The dressing and fastener will be CE marked by the legal manufacturer (Planet Medical Products Co. Ltd., China). The manufacturer is ISO13485 certified.

Hidramed AX fabric is an OEKO-TEX® certified material. The Hidramed AX full produced garment has been evaluated in accordance with ISO 10993 and it is biocompatible for its intended use. Verification and validation testing will be performed to evaluate the design of the garment. Hidramed Solutions will CE mark the device in accordance with the medical device directive 93/42/EEC.

CE-GAX001-01

V4.0

CR: 144

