6.3.4 Criteria for Withdrawal or Discontinuation

Subjects may withdraw from the study at any time without any rationale and without compromising their future medical care.

The subject may also be removed from the study by their physician or the consultant if they feel it is the best interest of the subject.

The use of the Hidrawear garment will be suspended if the patient presents with pyrexia and/or infection.

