6.4 Procedures

6.4.1 Pilot Study Procedures

Procedures & Assessments	Day 0	Day	Day	Day	Day	Day	V2;
	Enrolment	1 - 6	7	8 - 13	14	15 - 20	End of
	Assessment						Intervention
							Day 21
Informed Consent	X						
Medical / HS History	X						
Armpit Clinical assessment	X						X
Inclusion/exclusion criteria	Х						
Observe Subject using usual method of dressing wound	Х						
Dermatology Quality or life index survey, Ease of Use, Comfort, Time, Pain scale.	Х		Х		Х		Х
Subject trained on use of HidraWear Ax	Х						
Subject trained on use of Thermometer	Х						
Subject daily use of Hidrawear AX		Х	Х	Х	Х	Х	X
Temperature Record	Х	Х	Х	Х	Х	Х	Х
Observe Subject using Hidrawear AX							X
Daily Survey		Х	Х	Х	Х	Х	Х
Checkup phone call			Х		Х		
Researcher Data Entry	Х	Х	Х	Х	Х	Х	Х
Adverse Events	Х	Х	Х	Х	Х	Х	Х

CE-GAX001-01

V4.0

CR: 144

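### On Days 1–20 no daily question and no scheduled examination targets the local skin reactions that the protocol itself names

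*Combined protocol and SAP*

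**What the plan says.** **Named risks.** Section 2.4 states: "Potential side effects: Dermatitis, infection and skin irritation or skin abrasion". Section 4.1.1 lists a control against fibres retained in the wound: "Users instructed to carry out daily visual inspection of wound". Section 6.3.4 adds: "The use of the Hidrawear garment will be suspended if the patient presents with pyrexia and/or infection".

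**Daily contact.** Section 6.1.4 and Appendix 7 describe the same email: "Each day, at 1pm, subjects will receive an email requesting them to check in with the researcher by answering 3 questions". The first question is "What is your temperature", the second is "How many dressings did you use in the last 24 hours", and the third invites comments.

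**Examination.** In section 6.4.1 and Appendix 1 the row "Armpit Clinical assessment" is marked on Days 0 and 21 only. Section 4.6 agrees: "Users will be assessed by a Research Team member to establish that no infection is present in the wound site on enrolment and assessment".

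**Other contacts.** On Days 7 and 14 subjects complete the DLQI and questions on ease of use, comfort, pain and confidence. Both schedules also mark a check-up phone call on those two days, and mark adverse events in every column. Under sections 4.3 and 15.2 subjects stop using the device and contact the nurse if they have an adverse effect, may contact the nurse at any time, and may use the comment field.

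**The concern.** Section 3.4 says the pilot evaluates safety, and section 7.1 lists adverse events among the things it is meant to learn about. The expected events are mostly mild and local, and a prompt for temperature will not find them. Subjects are told to inspect the wound daily, yet no appended form asks what they saw. Local infection without fever would trigger the suspension in section 6.3.4, but nothing prompts for it specifically between visits.

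There may also be a reason to stay silent. Under section 4.3 a subject with an adverse effect stops using the device, and section 15.4 speaks of excluding subjects from the study. A subject who likes the garment might leave a mild rash out of an open comment box.

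At stake is what a low or zero count would mean. Section 4.1.1 rates irritation from the garment at likelihood 1 of 5, against 3 for adhesive dressings. A report of no skin reactions would seem to support that rating, but might partly reflect that nobody asked. Events missed this way cannot be recovered at analysis.

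**Working it through.** The plan states no figure on this point, so there is none to reproduce. The check sets the named risks against the routes of capture, then illustrates the size.

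**1. Routes of capture on Days 1–20**

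| Route | When | What it can detect |
|---|---|---|
| Temperature (Appendix 7) | Daily | Infection with fever |
| Dressing count (Appendix 7) | Daily | No skin sign |
| Open comment (Appendix 7) | Daily | Whatever the subject chooses to mention |
| DLQI question 1 (Appendix 6) | Days 7 and 14, one-week recall | Itch, soreness, pain or stinging anywhere on the skin |
| Pain and comfort (6.1.4) | Days 7 and 14 | Discomfort; not rash, broken skin or local infection |
| Check-up call (6.4.1, Appendix 1) | Days 7 and 14 | No content stated |
| Adverse event row (6.4.1, Appendix 1) | Every column | No method of asking stated |
| Self-inspection (4.1.1) | Daily | Visible signs, but no field for the result |
| Contacting the nurse (4.3, 15.2) | Any time | Whatever the subject reports |

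No row is a solicited question about dermatitis, irritation, abrasion or non-febrile infection in the axilla. DLQI question 1 feeds a sum score, and no rule turns a worse answer into an adverse event query. The appended Day 21 nurse form (Appendix 5) has no skin item either, although the armpit assessment is scheduled that day.

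**2. Days with the three-item form alone**

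Inputs: 23 subjects (6.3.9), 20 home days (6.3.8), and weekly questionnaires on Days 7 and 14.

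- Days per subject: 20 − 2 = 18.
- Planned subject-days: 23 × 18 = 414.
- If the 6 anticipated drop-outs (7.4) contribute nothing and are not replaced: 17 × 18 = 306.

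DLQI question 1 looks back over these days for symptoms. The count therefore describes the day's own contact and does not mean 414 days without any information.

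**3. Chance of recording no event**

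Let *p* be the true risk per subject and *c* the fraction of affected subjects captured. With 23 independent subjects, P(none recorded) = (1 − *pc*)^23. The documents give neither *p* nor *c*, so both are assumed and a range is shown.

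| Assumed true risk | *c* = 100% | *c* = 50% | *c* = 25% |
|---|---|---|---|
| 5% | 31% | 56% | 75% |
| 10% | 9% | 31% | 56% |
| 20% | 0.6% | 9% | 31% |

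For the middle row: 0.90^23 = 0.089, 0.95^23 = 0.307, 0.975^23 = 0.559.

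**4. What zero events could exclude**

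With zero events the one-sided 95% upper bound is 1 − 0.05^(1/n). That is 12.2% for n = 23 and 16.2% for n = 17, and it assumes that every event is captured. Under-capture widens a bound that is already wide.

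**The case against.** The strongest reply is that the plan asks more than the daily form suggests. DLQI question 1 on Days 7, 14 and 21, each with one-week recall, covers all of Days 1–21 for itch, soreness, pain and stinging. Pain and comfort are asked as well. The check-up call has its own row in the schedule, separate from the daily survey and the questionnaires, so its plain reading is two calls to every subject. Section 15.6 sends adverse event recording to an internal procedure (QP025) that is not supplied and may hold suitable forms. Safety is neither a listed objective (5.1) nor an endpoint (6.1.3).

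Much of this stands, and it rules out three stronger readings that a reader might infer:

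- *A reaction on Days 1–20 is recorded only if volunteered.* Not supported: symptoms are solicited on Days 7 and 14.
- *A reaction that clears before Day 21 leaves no trace.* Not supported: the weekly recall may pick it up.
- *Infection without fever has no planned means of detection.* Too strong: self-inspection and contact with the nurse are planned, though they depend on the subject.

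The reply does not supply a question aimed at the named reactions. The weekly items concern symptoms, in a disease that itself causes pain and soreness. Section 15.6 describes how an event is recorded once it occurs, and does not say how subjects are asked.

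**Conclusion.** The point holds as a gap in targeted capture. On Days 1–20 no daily question and no scheduled examination is directed at dermatitis, irritation, abrasion or non-febrile local infection, and the solicited skin information is weekly and non-specific. On about 414 planned subject-days (306 with six unreplaced drop-outs) the day's form is limited to temperature, dressing count and a comment.

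How much this under-counts is unknown. The rise in the chance of a clean record from 9% to 31% or 56% rests on an assumed 10% risk and assumed capture of 50% or 25%, and only illustrates the direction and possible scale. The supplied document shows that the method of asking is not described here; it does not show that no such method exists in the study's other procedures. The change is still worth making, because a cheap addition improves the safety data of a pilot that says it will evaluate safety.

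**What to change.** Add one fixed item to the daily check-in, for example: *At today's wound inspection, compared with Day 0, was there any new redness, rash, broken skin, sign of infection, or fibres in the wound? Yes/No; if yes, describe.* The nurse reviews each Yes as a possible adverse event. Ask the same item in the Day 7 and 14 calls. The daily survey already falls on Day 21, so no extra Day 21 form is needed.

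Reconcile the check-up call row in section 6.4.1 and Appendix 1 with section 6.1.4 and Appendix 7. The latter two describe emailed links and a call to non-responders, but not these calls.

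Reconcile the closing sentence of section 15.4, on excluding subjects after an adverse event, with sections 4.3 and 6.3.4, so that the effect of a reported reaction on participation is clear. More complete asking makes this more pressing.

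The cost is one tick-box on an existing form, which should still fit the stated time of under 5 minutes, plus ethics review of the amended form under section 10. The downside is more mild events to triage, some due to hidradenitis; with 23 subjects that is manageable.

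A tick for painkiller or fever medicine taken before the temperature reading is a separate, optional point about interpreting the temperature.

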26 REVISION HISTORY

Version history is managed and controlled by HidraMed Solutions' internal quality system.

Version	Reason for change	Changed by	Date
1.0	Initial Release	[name]	18 Oct 2019
2.0	New subject matter added detailing Reporting Guidelines for Serious Adverse Events, Adverse Events and Incidents per QP025 Clinical Evaluation Procedure and MEDDEV 2.12-1 GUIDELINES ON A MEDICAL DEVICES VIGILANCE SYSTEM. Removal of the requirement to Return Product.		26 Feb 2020
3.0	Section 4.6 updated to include a more detailed process flow and information relating to Subjects presenting with Pyrexia >38 Degrees.	[name]	09 Mar 2020
4.0	Protocol updated with changes to include a home visit for subjects when they cannot attend the clinic. Revision History section added to track changes throughout document life cycle		18 Mar 2020
